Study Design	
Multicenter, randomized, double-blind, placebo-controlled study evaluating the effect of CBP-201 in patients with CRSwNP whose disease remains inadequately controlled despite daily treatment with INCS therapy.
 
The study consists of 3 periods:
 
Screening/Run-in Period: (Up to 31 days)
 
Beginning at the first screening visit and throughout the duration of the treatment period, patients will be asked to standardize their INCS to a regimen of mometasone furoate (NASONEX®) nasal spray (MFNS) of 2 actuations (50 mcg/actuation) in each nostril twice daily (BID), total daily dose of up to 400 mcg, unless they are intolerant to BID INCS in which case, they may remain on a stable dosage of mometasone of 2 actuations (50 mcg /actuation) in each nostril once daily, total daily dosage of 200 mcg. The screening period can be up to 31 days to allow for a run-in of at least 28 days if the

	
patients have not been on a documented steady dose of INCS prior to screening. If the patients are able to document steady use, then the run-in period may be shortened to as little as 7 days (with patient diary entry to confirm compliance).
 
Treatment Period: (CBP-201/placebo for 24 weeks)
 
After screening/run-in has been completed, eligible patients will be randomly allocated in a 1:1:1 ratio to receive double-blind treatment with CBP-201 or placebo with every other week visits to the study site for subcutaneous (SC) injections:
 
 CBP-201 300 mg every 2 weeks SC administration for 24 weeks with an initial loading dose of 600 mg at Day 1 CBP-201 300 mg every 4 weeks SC administration for 24 weeks with an initial loading dose of 600 mg at Day 1. These patients will also receive volume matched placebo every 4 weeks on alternating visits to maintain the study blind. Placebo every 2 weeks SC administration for 24 weeks (Placebo loading at Day 1) 
Randomization will be stratified by comorbid asthma.
 
All patients will continue stable dose of MFNS (200 mcg) BID or once daily used during run-in period throughout the study.
 
Post-treatment Follow-up Period: (8 weeks)
 
After completing 24 weeks of treatment with the investigational product (IP) (or following early discontinuation of IP), patients will be followed for additional 8 weeks. Patients will be asked to complete a study visit every 4 weeks for follow-up assessments.

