	
7 DAYS of MFNS use in the 7 days prior to randomization AND at least 5 of 7 DAYS of NCS completion in the patient diary in the 7 days prior to randomization.
 
 6. Male patients who are non-sterilized and sexually active with a female partner of childbearing potential agree to use highly effective contraception from randomization until 8 weeks after last dose. 7. Female patients of childbearing potential who are sexually active with a nonsterilized male partner should have a confirmed negative serum beta-human chorionic gonadotropin test at Visit 1 and agrees to use highly effective contraception from signing of informed consent throughout the duration of the study and for 8 weeks after last dose. 8. Patient is able to understand and willing to sign the informed consent form (ICF) prior to any study related procedures being performed. 9. Willing and able to comply with all study visits and study-related procedures, in the opinion of the Investigator. 
Exclusion Criteria
 
A patient who meets any of the following criteria will be ineligible to participate in this study:
 
 10. Patients unable to use MFNS. 11. Patients who are taking or have taken the following prohibited therapies as specified: 
 a. Systemic steroids within 28 days prior to screening, b. Other nonbiologic investigational drugs within 60 days (or 5 half-lives, whichever is longer) of screening, c. Intranasal corticosteroid drops or corticosteroid-administering devices (eg, OptiNose device or stents) within 28 days prior to screening, d. Non-steroidal immunosuppressants (eg, cyclosporine, methotrexate, azathioprine, mycophenolate, sirolimus, tacrolimus) within 60 days or 5 half-lives, whichever is longer, of screening, e. Any monoclonal antibody therapy (eg, benralizumab, mepolizumab, omalizumab, resizumab, dupilumab) or investigational biologic drug for asthma or other diseases within 60 days or 5 half-lives, whichever is longer, of screening, f. Leukotriene antagonists/modifiers within 7 days prior to screening for patients who were not on continuous treatment for \geq 30 days prior to screening, g. Allergen immunotherapy for patients who were not on maintenance treatment for at least 90 days prior to screening, h. Any marketed nonbiologic drug that modulates type 2 cytokines (eg, suplatast tosilate) within 30 days or 5 half-lives (whichever is longer) prior to screening, i. Any investigational small molecule drug or treatment within 16 weeks or 5 half-lives (whichever is longer) prior to screening. 12. Patients who did not respond favorably to previous dupilumab treatment (eg, therapy failure or patient experienced an adverse reaction to treatment). 13. Patients who have undergone any nasal surgery (including polypectomy) within 6 months before screening; or have a history of sinus or nasal surgery modifying the structure of the nose such that assessment of NPS is not possible or have had uncontrolled epistaxis requiring surgical or procedural intervention, including nasal packing.

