--	--

	
 14. Patients with conditions/concomitant diseases making them non evaluable at screening or for the primary efficacy endpoint such as: antrochoanal polyps, nasal septal deviation that would occlude at least 1 nostril, acute sinusitis, nasal infection or upper respiratory infection at screening or within 2 weeks before screening, ongoing rhinitis medicamentosa; known or suspected diagnosis of cystic fibrosis; chronic granulomatous disease and granulomatous vasculitis, granulomatosis with polyangiitis (Wegener's Granulomatosis), eosinophilic granulomatous with polyangiitis (Churg-Strauss syndrome), Young's syndrome, primary dyskinetic ciliary syndromes (eg, Kartagener's syndrome) or other dyskinetic ciliary syndromes. 15. Signs or a CT scan suggestive of Allergic Fungal Rhinosinusitis 16. Patients with co-morbid asthma are excluded if: 
 a. Forced Expiratory Volume in 1 second (FEV₁) ≤ 50% of normal predicted value OR b. An exacerbation within 90 days prior screening that required hospitalization (> 24 hours) OR c. Are on a daily dose of inhaled corticosteroids (ICS) higher than 1000 mcg fluticasone propionate or the equivalent. 17. Known or suspected history of immunosuppression, including history of invasive opportunistic infections, such as aspergillosis, coccidioidomycosis, histoplasmosis, human immunodeficiency virus (HIV), listeriosis, pneumocystosis, or tuberculosis, despite infection resolution; or unusually frequent, recurrent or prolonged infections. Tuberculosis testing would be performed on a country-by-country basis according to local guidelines if required by regulatory authorities or ethics committees. 18. Patients who have active Hepatitis B, Hepatitis C or HIV infections as determined by positive results at Screening for hepatitis B surface antigen (HBsAg) or hepatitis B core antibody (HBcAb); or hepatitis C virus antibody (HCVAb); or positive HIV serology. Note: Patients who test positive for HBcAb, negative for HBsAg and subsequently confirmed positive for HBsAb, indicating resolved natural infection (confirmed by negative HBV-DNA), may participate. Patients with positive HCVAb may participate if subsequent viral load is confirmed negative. 19. A helminth parasitic infection diagnosed within 24 weeks prior to the date of informed consent that has not been treated, or has failed to respond to, standard of care therapy. 20. Evidence of infection requiring treatment with systemic antibacterials, antivirals, antifungals, antiparasitics, or antiprotozoals within 7 days before baseline, or viral infections within 14 days before screening that may not have received antiviral treatment. 21. Live, attenuated vaccinations within 28 days prior to screening or planned live, attenuated vaccinations during the study. 22. Pregnant or intent to become pregnant during the study, or breast-feeding women. 23. Any disorder, including, but not limited to, cardiovascular, gastrointestinal, hepatic, renal, neurological, musculoskeletal, infectious, endocrine, metabolic, haematological, psychiatric, or major physical impairment that is not stable in the

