4.4 Other Concomitant Medications

Patients will maintain regular treatment with INCS and should continue on a stable dose and schedule throughout the study and dose adjustment is not allowed.

Patients with comorbid asthma may also be currently taking inhaled corticosteroid (ICS) and should continue on a regular dose and schedule throughout the study. In the interests of the patients' safety and acceptable standards of medical care, the Investigator will be permitted to prescribe any treatment(s) at their discretion. All treatments, including prescription drugs, vitamins, or herbal medications taken within 28 days prior to Screening (Visit 1) and throughout the trial must be recorded in the source documents and eCRF, including indication, dose, unit, route, frequency, and start and stop dates of administration.

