4.5 Prohibited Medications and Restrictions

- Intranasal corticosteroid drops or CS-administering devices (eg, or OptiNose device or stents) are prohibited. Only mometasone furoate (NASONEX[®]) nasal spray (MFNS) or regional equivalent, if agreed with the medical monitor, will be permitted during the study as a nasal treatment.
- Patients may not use any marketed biologic drug (eg, omalizumab, benralizumab, mepolizumab, reslizumab, dupilumab) within 60 days or 5 half-lives (whichever is longer) of screening and throughout the study.
- Non-steroidal immunosuppressants (eg, cyclosporine, methotrexate, azathioprine, mycophenolate, sirolimus, tacrolimus) are not permitted during the study.
- Leukotriene antagonists/modifiers for patients who were not on continuous treatment for ≥ 30 days prior to screening are prohibited taken within 7 days prior to screening. If the patients were on these medications for ≥ 30 days prior to screening they may continue on a stable dose and schedule.

- Patients may not initiate treatment with allergen immunotherapy from screening throughout the duration of the study; if they have been on maintenance allergen immunotherapy for at least 90 days prior to screening, they may stay on a stable dose of this therapy during the study and dose adjustment is not allowed.
- Patients may not use any marketed nonbiologic drug that modulates type 2 cytokines (eg. suplatast tosilate) within 30 days or 5 half-lives (whichever is longer) prior to screening and throughout the study.
- Patients may not use any investigational small molecule drug or treatment within 16 weeks or 5 half-lives (whichever is longer) prior to screening and throughout the study.
- From V1 and throughout the study, patients may not use locally administered nasal decongestants except for the purpose of study required nasal endoscopy.

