### 4.2 Definitions

#### Age at Baseline

Age will be calculated using the date of birth and date of the baseline visit as below:

Integer part of [(Date of Baseline Visit – Date of Birth) / 365.25]

Baseline

Unless otherwise specified, baseline is defined as the last non-missing value prior to the first dose of study drug. If time is not collected but the assessment is performed on the same day as the first dose of study drug, it would be considered as baseline.

Baseline Week

For weekly average analysis, baseline week is defined as 7 days prior to the baseline visit (Study day ranges from -7 to -1).

Change from Baseline

Change from baseline is defined as post-baseline value minus baseline value.

Study Day 1

Study day 1 is defined as the date of randomization for untreated randomized subjects or the date of first dose for treated subjects.

Study Day

Study Day will be calculated relative to the date of randomization for untreated randomized subjects and relative to the date of first dose for treated subjects.

If event is prior to the first dose, then study day is calculated as:

$$\text{Date of Event} - \text{Date of First Dose}$$

If event is after the first dose, then study day is calculated as:

$$\text{Date of Event} - \text{Date of First Dose} + 1$$

Duration of Treatment

Duration of Treatment (days) will be calculated as:

$$\text{Last Date of Dose} - \text{First Date of Dose} + 1$$

Treatment-Emergent Adverse Events

Treatment-emergent adverse events are defined as any adverse events occurred or worsen during the treatment-period, whether considered related to the treatment.

Where the AE start date is missing, adverse events will be assumed to be treatment-emergent, unless there is clear evidence (through comparison of partial dates) to suggest that the adverse event started prior to the first dose of study treatment.

Prior and Concomitant Medication

Prior and concomitant medication is defined as any medications that started before the first dose of study drug and stops on or after the first dose of study drug.

Prior Medication

Prior medication is defined as any medications that started and stopped before the first dose of study drug.

Concomitant Medication

Concomitant medication is defined as any medications that started on or after the first dose of study drug.

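### Exclusion 11a stops at screening, so a systemic steroid course in the 7-to-31-day run-in does not bar randomisation and can shift the co-primary baselines

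*Protocol*

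**What the plan says.** **Steroid window.** Exclusion 11a (Protocol Synopsis and 5.2) excludes "Systemic steroids within 28 days prior to screening".

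**Length of the gap.** The Synopsis states that "The screening period can be up to 31 days". The note to inclusion criterion 4 allows a run-in of 7 to 31 days.

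**Rules during the run-in.** Protocol 4.5 prohibits steroid drops and steroid-delivering devices and, from Visit 1 onward, local nasal decongestants outside study endoscopy. It does not mention systemic steroids. Protocol 4.3 lists a short systemic course among rescue options, and 4.4 says "the Investigator will be permitted to prescribe any treatment(s) at their discretion".

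**Checks at Visit 2.** Eligibility is verified again before randomisation. NPS must again be at least 5, with at least 2 per nostril, if endoscopy is done, and weekly NCS must exceed 1.

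**Baselines.** Protocol 7.8.1 takes the Visit 2 central reading as the NPS reference. If Visit 2 falls within 7 days of Visit 1, endoscopy is normally not repeated. For the diary score, SAP 4.2 says "baseline week is defined as 7 days prior to the baseline visit", that is Days -7 to -1.

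**Infection.** Exclusion 14 names "nasal infection or upper respiratory infection at screening or within 2 weeks before screening" as one example in an open list. Exclusion 20 excludes "Evidence of infection requiring treatment with systemic antibacterials, antivirals, antifungals, antiparasitics, or antiprotozoals within 7 days before baseline".

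**The concern.** Both co-primary endpoints are changes from baseline, so whatever moves baseline moves the endpoint. If a steroid course shortly before Day 1 lowers NPS or NCS for a time, the patient starts from an artificially good value. When the effect wears off, the rise offsets real improvement. Exclusion 11a presumably exists to prevent this, yet its window closes at Visit 1 and the baselines are measured afterwards.

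The omission stands out because most other windows in criterion 11 that end at screening have a counterpart in 4.5 that carries the restriction forward: steroid drops and devices, immunosuppressants, biologics, type 2 cytokine modulators and investigational small molecules. Item 11a has none. At stake are avoidable noise in both co-primaries and by-arm mean changes that are harder to read.

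**Working it through.** **1. The plan's own scale.** Inputs from Protocol 9.1: difference 1.3, SD 2.1, two-sided alpha 0.05, power 80%.

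- n per group = 2 × (1.960 + 0.842)² × 2.1² / 1.3² = 40.96, so 41.
- With 15% dropout: 41 / 0.85 = 48.2, so 49 per group and 147 in total.

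The stated figures reproduce. The 1.3-point target is used below only as a yardstick.

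**2. Days not covered.** Let L be the days from Visit 1 to Day 1.

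- Systemic steroids: 11a covers none of the run-in, so L days are open, from 7 to 31.
- Infection needing systemic anti-infectives: exclusion 20 covers the last 7 days, so max(0, L − 7) days are open. This gives 0 for L = 7, 7 for L = 14, 21 for L = 28 and 24 for L = 31. Days -7 to -1, the NCS baseline week, are covered.
- Infection not needing them: no dated rule reaches past Visit 1, because the viral clause of exclusion 20 also ends at screening.

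**3. Does the Visit 2 check close the steroid gap?** Re-applying 11a at Visit 2 looks back from screening and gives the same answer as before. The score thresholds are floors:

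- An NPS fall of d points passes if the earlier score was at least 5 + d and each side stays at 2 or more. From the maximum of 8, a fall of up to 8 − 5 = 3 can pass. From 5, none can.
- Weekly NCS can fall from 3 to just above 1, almost 2 points, and pass.

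**4. Which baselines are exposed?**

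- Visit 2 within 7 days of Visit 1: the NPS baseline is normally the Visit 1 reading and precedes any run-in course. The NCS week remains exposed.
- Visit 2 later than that: both are exposed.

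**5. Size.** The documents give neither the frequency of run-in courses nor their effect on scores. One affected patient whose baseline is shifted by d moves the unadjusted mean change of an arm of n by d / n. Assuming d = 1 to 2 NPS points:

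- n = 49 (planned): 0.02 to 0.04 points, or 2% to 3% of 1.3.
- n = 10 (assumed): 0.10 to 0.20 points, or 8% to 15% of 1.3.
- n = 5 (assumed): 0.20 to 0.40 points, or 15% to 31% of 1.3.

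The arm sizes reached are not in the documents; SAP 4.15 says only that the sample is small. In the planned mixed model, which adjusts for baseline, the same shift leaves b × d per affected patient, where b is the slope of the Week 24 score on baseline. This is less than d whenever b is between 0 and 1. The documents give no value for b.

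**The case against.** **Safeguards on steroids.** Concomitant medication is reviewed at Visit 2, and 4.3 asks for a site visit with endoscopy before systemic steroids start, so the investigator would usually know of a course. The opening words of criterion 11 cover patients who are taking a listed therapy, which might reach current use at Visit 2. Exclusions 23 and 24 allow discretionary exclusion, and 24 expressly spans the run-in. The score thresholds remove some steroid responders. All of this stands as mitigation, but none of it closes the gap. Knowing of a course does not make it an exclusion. Criterion 11 refers back to the windows as specified, and a course finished before Visit 2 is not current. Exclusion 24 concerns examination, vital-sign and laboratory findings, not medication use, and 23 concerns unstable disorders.

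**Infection.** A reader might infer that any patient infected during the run-in is eligible. The documents do not support that. The dated infection item in exclusion 14 is only an example; the governing words also cover conditions that make a patient unevaluable on the primary endpoint, and that limb has no screening cut-off. Exclusion 20 covers infections needing systemic anti-infectives during the NCS baseline week. What remains is infection not needing such treatment, for example an untreated cold, where the dated example and the general limb of exclusion 14 point different ways.

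**Power.** A reader might also want a figure for lost power. Any such figure would rest on an invented frequency and effect size. An unadjusted calculation would generally overstate the loss under the planned baseline-adjusted model, and SAP 4.15 has since withdrawn hypothesis testing.

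**Conclusion.** The steroid gap is real: the whole run-in, 7 to 31 days, lies outside 11a, and no other rule expressly makes a course in that period an exclusion. The consequence is noise in the co-primary baselines. A reader might infer a biased treatment comparison, but the events precede randomisation and so do not favour an arm on average.

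The size is unknown from the documents. It is probably small under the planned mixed model. It is more visible in the by-arm descriptive change from baseline, the only efficacy summary SAP 4.15 keeps, where one patient could move a very small arm by a few tenths of a point under the assumptions shown. This supports an inexpensive wording change; it does not call the design into question. The infection part is limited to infections not needing systemic anti-infectives and is a matter of reconciling exclusions 14 and 20.

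**What to change.** 1. **Exclusion 11a (Synopsis and 5.2).** Reconcile it with 4.3, 4.4 and 4.5, and anchor the window to randomisation as well as screening. A patient who takes a systemic course after Visit 1 becomes a screen failure and may be re-screened under 5.3, at least 28 days after the original screening date. This sets eligibility only; it does not restrict what an investigator may prescribe.

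2. **Exclusions 14 and 20.** Reconcile the screening-dated infection example in 14 with that criterion's own primary-endpoint limb and with the baseline-dated clause of 20, so that sites know how an infection not needing systemic anti-infectives before Day 1 is handled.

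3. **Patients already randomised.** New eligibility wording cannot reach them. Flag run-in systemic steroid use beside the descriptive co-primary tables. Protocol 4.4 already requires medications to be recorded throughout. The flag is needed because SAP 4.2 classes a course that ended before the first dose as prior medication, and the summaries named in SAP 4.9 cover concomitant and prior-and-concomitant use, leaving prior-only use to the listings.

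**Cost.** One clause in 11a, a clarification of 14, and a footnote or listing flag. A few patients would be delayed or re-screened. Since 11a would also apply at the new screening visit, a course ending on run-in day k puts re-screening at about day k + 28, so up to about day 59 after the original screening when k = 31.

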- n. PK blood samples should be collected prior to dosing; date and clock time for each sample should be recorded.
- o. PD blood samples for biomarkers of inflammation include Eotaxin-3, eosinophil cationic protein, total immunoglobulin E, thymus and activation-regulated chemokine, and periostin. Blood eosinophil count will be measured as part of hematology test. C-reactive protein will be determined as part of the serum chemistry.
- p. ADA blood sample: NAb will be tested at all ADA collection time points in samples that are ADA positive.

Suzhou Connect Biopharmaceuticals, Ltd

Protocol CBP-201-WW003

Investigational Drug: CBP-201

21 December 2021

- q. Patients are to be observed for 2 hours postdose on D1 (V2), W2 (V4), and W4 (V5), and 30 minutes postdose for W6 (V6) and beyond. Assessments and testing should be completed predose except as noted otherwise. Rotate injection sites: abdomen (avoid area proximal to umbilicus), outer thigh, and upper arm (lateral or posterolateral). Only 1 mL should be injected per site, and an injection site should not be in the same anatomical location used during the previous visit.
- r. Dispense albuterol/salbutamol MDI for reversibility testing and as an optional take-home rescue medication for those patients with asthma. Patients should be offered replacements as needed for symptom control throughout the study and should be reminded to document the use in their patient diary. Sites may also provide MFNS for required concomitant use as needed.
- s. Injection site reactions should be assessed at all visits from the first dosing day until the end of the study. The previous injection site(s) should be assessed prior to dosing. On all dosing days, the new injection site should be assessed prior to the patient's release. The SC injection site may be assessed using a standard instrument provided in Appendix or described as needed by the Investigator in the medical notes. Clinically significant findings as determined by the Investigator will be reported as an AE. See section 8.6 for more details.
- t. Unscheduled visits may be conducted as needed, and additional assessments performed at these visits are at the discretion of the Investigator.
- u. CT scan will only be required for subjects that are enrolled at Study Sites that are approved and qualified to perform CT Scans.

Suzhou Connect Biopharmaceuticals, Ltd

Protocol CBP-201-WW003

Investigational Drug: CBP-201

21 December 2021

LIST OF ABBREVIATIONS

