3.4 Post-treatment Follow-Up Period: 8 weeks

After completing 24 weeks of treatment with the investigational product (IP) (or following early discontinuation of IP), patients will be followed for additional 8 weeks. Patients will be asked to complete a study visit every 4 weeks to:

- Evaluate PK, PD, antidrug antibodies (ADA), physical examination, QOL, efficacy, safety, and a last endoscopy at the end of study
- Continue to complete patient diary for symptom evaluation
- Continue MFNS stable dose during post-treatment period
- Report any AE

Patients will be encouraged to remain in the study even if discontinued from study drug treatment. Patients who discontinue prematurely from study drug treatment are assessed as soon as possible using the procedures normally planned for the End of Treatment Visit and the 2 post-treatment Follow-up Period Visits.

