6.15 Visit 15 (End of Treatment) (Study Day 169 ± 3 days/Week 24)

The following assessments and procedures should be completed in the order given below, if possible:

- Review and record changes in of concomitant medications
- Vital sign measurements
- Brief physical exam
- Review of patient diary and NPIF data
- Record body weight
- CT scan (only required for subjects that are enrolled at Study Sites that are approved and qualified to perform CT Scans)
- NCS assessment

Suzhou Connect Biopharmaceuticals, Ltd

Protocol CBP-201-WW003

Investigational Drug: CBP-201

21 December 2021

- EQ-5D-5L assessment
- VAS-rhinosinusitis assessment
- SNOT-22 assessment
- TNSS assessment
- UPSIT assessment of smell
- Nasal endoscopy and NPS scoring
- Pulmonary Function Tests (Spirometry) for patients with comorbid asthma only
- Healthcare resource utilization questionnaire
- 12-lead ECG
- Urine pregnancy test
- Safety laboratory samples (hematology, serum chemistry, urinalysis)
- PK blood sample (predose)
- PD blood sample (predose)
- ADA blood sample (predose)
- Administer study drug
- Injection site assessment
- Dispense optional take-home rescue medications (albuterol/salbutamol) to patients with asthma, if needed. Remind patients to document the use in their patient diary.
- AE review and recording

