6.19 Early Termination Visit

Should a patient withdraw consent or be withdrawn from the study for any reason after randomization, every effort should be made to schedule a final visit, during which the following assessments and procedures should be completed in the order given below, if possible:

- Review and recording of changes in concomitant medications
- Vital sign measurements
- Body weight recorded
- CT scan (only required for subjects that are enrolled at Study Sites that are approved and qualified to perform CT Scans)
- NCS assessment
- EQ-5D-5L questionnaire
- VAS-rhinosinusitis assessment
- SNOT-22 assessment
- TNSS assessment
- UPSIT assessment of smell
- Nasal endoscopy and NPS scoring
- Pulmonary function tests (Spirometry) for patients with comorbid asthma only
- Healthcare resource utilization questionnaire
- Complete physical examination
- 12-lead ECG
- Urine pregnancy test
- Safety laboratory samples (hematology, serum chemistry, urinalysis)

- PK blood sample
- PD blood sample
- ADA blood sample
- Collect the daily patient handheld device
- AE review and recording

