**Table 2. Analysis Window for CT Scan**

Nominal Visit	Analysis Visit	Target Study Day	Minimum Study Day	Maximum Study Day
Visit 2	Baseline	1	-30	1
Visit 15	Week 24 (End of Treatment)	169	166	172

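### At CT-qualified sites the Early Termination visit lists a sinus CT even when a post-baseline CT has already been taken; after the Week 24 scan, no stated analysis uses it

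*Protocol*

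**What the plan says.** **When CT is listed.** The planned scans are at screening (Protocol 6.1) and Visit 15 (6.15, Day 169 ± 3). Sections 6.16 (Week 28) and 6.17 (Week 32) list none. Section 6.19 adds one at Early Termination: "CT scan (only required for subjects that are enrolled at Study Sites that are approved and qualified to perform CT Scans". The visit applies when patients "withdraw consent or be withdrawn from the study for any reason after randomization", and its list is introduced with "the following assessments and procedures should be completed in the order given below, if possible". Table 1 footnote u repeats the site limit: "CT scan will only be required for subjects that are enrolled at Study Sites that are approved and qualified to perform CT Scans". Neither place mentions study day or an earlier scan.

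**Stopping drug early.** Under Protocol 3.4, patients who stop drug are "assessed as soon as possible using the procedures normally planned for the End of Treatment Visit", followed by two follow-up visits. The End of Treatment list in 6.15 includes the CT.

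**How CT is analysed.** The CT endpoints are secondary and are changes from baseline at Week 24 (Protocol 3.9.2, SAP 3.3.1.2). The SAP's "Table 2. Analysis Window for CT Scan" has two rows: baseline (Days -30 to 1) and Week 24 (Days 166 to 172). There is no Early Termination analysis visit. SAP 4.11.1.2 does not impute secondary endpoints, whereas Protocol 5.8 would carry the last observation forward, where feasible, for patients taken off study drug early. SAP 4.15 records the decision to stop the trial early and leaves the CT measures out even of the listings.

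**The concern.** A research scan exposes the patient to X-rays, so each one should have a stated purpose. The scheduled CTs do. The Early Termination CT is written so that having been scanned already makes no difference. The clearest case is a patient who has completed treatment, had the Week 24 CT, and then withdraws during follow-up: leaving triggers a scan that staying would not. The protocol avoids needless repetition elsewhere, since endoscopy is normally not repeated at Visit 2 when Visit 2 is within 7 days of Visit 1 (7.8.1). CT has no comparable rule.

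At stake are a small number of avoidable scans, each also sent for central reading (7.8.5), and an unclear instruction to sites.

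**Working it through.** **Step 1: the SAP window.** Target Day 169 with the ± 3 days of Visit 15 gives 169 - 3 = 166 and 169 + 3 = 172, as in SAP Table 2. The window has 172 - 166 + 1 = 7 days.

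**Step 2: follow each path at a CT-qualified site.**

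| Path | Post-baseline CTs listed | Place in SAP Table 2 |
|---|---|---|
| Completes Week 32 | Visit 15 | Week 24 |
| Has Visit 15 CT, leaves in follow-up | Visit 15 and Early Termination | First: Week 24. Second: none after Day 172 |
| Stops drug, scanned at once, leaves later | End of Treatment and Early Termination | Only a scan on Days 166 to 172 |
| Leaves before Day 166, no earlier post-baseline CT | Early Termination | None, though Protocol 5.8 would carry it forward |
| Leaves on Days 166 to 172, no scan in the window | Early Termination | Week 24 |

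**Step 3: look for another use of the second scan in row 2.** CT is not a safety endpoint (Protocol 3.9.6, SAP 3.3.1.6). With only one post-baseline CT visit, a repeated-measures model has no other visit to borrow from. Carry-forward under 5.8 does not help, because Week 24 is already observed. I find no use.

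**Step 4: spacing.** From Day 169 to the Visit 17 target, Day 225, is 56 days, or 8 weeks, so the extra scan follows the Week 24 scan by at most about 8 weeks. The screening scan precedes Day 1 and is thus more than 168 days, or 24 weeks, before Day 169.

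**Step 5: scale.** Take Days 2 to 224, from the day after first dose to the day before the Visit 17 target: 224 - 2 + 1 = 223 days.

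- Before the window: 165 - 2 + 1 = 164 days (73.5%)
- Inside it: 7 days (3.1%)
- After it: 224 - 173 + 1 = 52 days (23.3%)

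The planned dropout allowance (Protocol 9.1) gives 0.15 × 147 = 22.05 patients. Expected scans after the window = 22.05 × share at CT sites × 52/223:

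- share 25%: 1.29
- share 50%: 2.57
- share 100%: 5.14

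The documents give neither the share at CT sites nor the timing of withdrawals. The formula assumes an even spread, that every dropout attends the visit, and that each late leaver already has a Week 24 CT. It does not count repeats in patients who stopped drug early.

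**The case against.** Several points on the other side stand.

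- **The requirement is limited.** It applies only at qualified sites, and the whole list is to be done if possible. A reader might infer that every Early Termination visit carries a compulsory CT; the text does not say so.
- **Scans before Week 24 are not simply wasted.** A reader might go further and infer that nearly all Early Termination scans are useless, since 164 + 52 = 216 of 223 days lie outside the window. The documents do not support this. A share of calendar days is not a probability, a scan on Days 166 to 172 does count, and Protocol 5.8 states a use for a scan before Week 24. The SAP contradicts 5.8, and Protocol 9.7 leaves missing-data handling to the SAP, but that is a conflict to settle. It does not show that the scan has no purpose.
- **Moving an early drug-stopper's scan to Week 24 is not clearly possible.** Section 3.4 describes an immediate End of Treatment assessment and two follow-up visits, while 5.6 expects all study procedures to be completed after drug is stopped for treatment failure. Whether such a patient has a Week 24 visit is unclear.
- **The mapping gap is general.** The SAP defines no Early Termination analysis visit for any assessment.
- **The analysis side is now moot.** Under SAP 4.15 no CT measure is analysed or listed. A reader might also infer that the early stop sent all ongoing patients through this scan; the documents do not say whether that happened.

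None of this supplies a use for a scan taken after the Week 24 CT.

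**Conclusion.** The point holds in a narrow form. At CT-qualified sites, the protocol lists a repeat CT for a patient who already has the Week 24 scan and leaves during follow-up, and neither document uses the result. That conclusion needs no numerical assumption. A patient scanned on stopping drug who later leaves is also listed for a repeat; under the SAP that repeat counts only if it falls on Days 166 to 172, and under Protocol 5.8 it could be the value carried forward.

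The number of scans cannot be derived from the documents. About 1 to 5 after the Week 24 window is an illustration under the assumptions in the working. No radiation dose is given, so the burden can be expressed only as a count of scans. The defect lies in the protocol and SAP as planned; correcting it would not change the final report, given SAP 4.15.

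**What to change.** In Table 1 footnote u and Protocol 6.19, state that the Early Termination CT is not done if a post-baseline CT has already been taken, unless the visit falls on Days 166 to 172 and no scan has yet been taken in that window. The exception matters: without it, a patient scanned on stopping drug and leaving on, say, Day 168 would lose a scan that SAP Table 2 accepts.

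Separately, reconcile Protocol 3.4, 5.6, 5.8 and 6.19 with SAP Table 2 and 4.11.1.2. They should say whether a patient who stops drug early has a Week 24 visit, and whether a scan before Week 24 is analysed, carried forward or left out. Settle this together with the exemption, because if 5.8 were kept, omitting a later repeat would change which scan is carried forward.

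The first change costs one footnote and one list item in an amendment and loses no scan that SAP Table 2 uses. The second touches several sections of both documents and needs a decision from the sponsor.
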